#### EASI score.

0 = clear

0.1 - 1.0 = almost clear

1.1 - 7.0 = mild

7.1 - 21.0 = moderate

21.1 - 50.0 = severe

50.1 - 72.0 = very severe

#### VAS score:

0 = no pruritus

>0 – <4 points = mild pruritus

>4 – <7 points = moderate pruritus

>7 - <9 points = severe pruritus

>9 points = very severe pruritus

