12.9 Visual Analog Scale (VAS)

VAS will be performed as a measure of pruritus at the times indicated in the Time and Events Table (Appendix A). Subjects will be asked to report their pruritus symptoms over the 24 hrs period before the visit.

VAS score can be found in Appendix F.

[figure not shown]
The following VAS categories will be used:

0=no pruritus

>0-<4 points=mild pruritus

≥4–<7 points=moderate pruritus

≥7–<9 points=severe pruritus ≥9 points=very severe pruritus

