#### 4.3.1. EASI, IGA, VAS

EASI, IGA, and VAS scores will be summarized using descriptive statistics at Baseline, Day 14, Day 28, and Day 42 for actual values and change-from-baseline values. Tabulations will be produced for both the ITT and PP populations.

The difference in treatment groups in change-from-baseline values at post-baseline visits will be analyzed using a mixed model Analysis of Variance with one between-subject variable (active group vs. vehicle group) and one within-subject variable (Day 14, Day 28, and Day 42).

The interaction between within-subject and between-subject variable will be included in the mixed model to test if any difference in treatment groups at post-baseline visits.

The model will include treatment group, siteid and visit as the independent effects and the interaction term treatment group\*visit\*siteid. Outputs from the analysis will include the p-value

for the treatment group and interaction factor separately. The p-value should be evaluated at a significance level of 0.05.

Mixed model ANOVA will be implemented using PROC GLM in SAS using the REPEATED option.

Additionally, a one-sided two-sample equal-variance t-test will be performed as a supportive test to analyze the differences in mean change in scores from baseline between treatment groups at each post baseline visit (Day 14, Day 28, Day 42). Output from the analysis will include a one sided 95% confidence interval and p-value. The p-value should be evaluated at a one-sided significance level of 0.025.

The above analysis will also be performed by subgroups – age, gender, and race for the ITT Population.

An exploratory analysis will also be conducted by the number of AD sites (1, 2 and >2) the subjects had.

At each visit, based on the score, subjects will be categorized into the below categories.

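### As printed, the SAP's pruritus VAS bands leave scores of exactly 4, 7 and 9 without a category, and the SAP does not say how to handle them

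*SAP*

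**What the plan says.** SAP section 4.3.1 states the rule: "At each visit, based on the score, subjects will be categorized into the below categories". For the VAS, after a category for a score of 0, the SAP prints four bands:

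- ">0 – <4 points = mild pruritus"
- ">4 – <7 points = moderate pruritus"
- ">7 - <9 points = severe pruritus"
- ">9 points = very severe pruritus"

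Protocol section 12.9 has the same categories and cut points, but includes the lower bound in the top three bands: "≥4–<7 points=moderate pruritus", "≥7–<9 points=severe pruritus" and "≥9 points=very severe pruritus".

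The bands feed the VAS shift tables from baseline to each post-baseline visit: 14.2.4.1 (ITT), 14.2.4.2 (PP), and 14.2.4.3 to 14.2.4.5 (gender, age category, race). The shell has the five pruritus categories plus Missing and Total. SAP section 3.2 describes the extra category in categorical summaries as one for missing data. SAP section 5, on changes to planned analyses, covers the per-protocol definition and the deferral of biomarker and microbial data. It does not mention the VAS bands.

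**The concern.** A classification applied to every subject at every visit should give each possible score exactly one category. As printed, the SAP's bands do not. The three values left out are round numbers, which a respondent or a rounding rule may well favour.

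The SAP also does not say what happens to a recorded score that fits no band. A programmer following the text could let the record drop out, show it under Missing, or let a default branch assign it. These choices give different tables. Dropping the record shrinks the denominator. Showing it as Missing mixes a recorded score with real dropout, for which the plan allows 20% and makes no imputation. A default branch puts the score wherever the code happens to end: a chain whose last branch is very severe would put 4, 7 and 9 all there.

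A gap at baseline carries forward. A subject whose baseline score is exactly 7 or 9 has no severity row in the Day 14, Day 28 or Day 42 table.

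**Working it through.** The plan gives no figure to reproduce, so the check is one of coverage: apply each set of bands as printed to every possible score and list the scores that get no category.

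**Inputs.** SAP bands from section 4.3.1; protocol bands from section 12.9; the entry criterion of a VAS of at least 5 from protocol section 6.2. The range of 0 to 10 and the step size are assumptions, because the scale is a figure that is not reproduced in the text and neither document states its resolution.

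**Step 1: the cut points.**

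| Score | SAP band ending here | SAP band starting here | SAP category | Protocol category |
|---|---|---|---|---|
| 4 | mild, below 4 | moderate, above 4 | none | moderate |
| 7 | moderate, below 7 | severe, above 7 | none | severe |
| 9 | severe, below 9 | very severe, above 9 | none | very severe |

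**Step 2: all other scores.** On a 0 to 10 grid in steps of 1, 0.5 and 0.1, the scores with no SAP category are 4, 7 and 9 each time. Every other score gets the same category under both documents. The protocol bands leave no score unclassified.

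**Step 3: share of possible values.**

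| Step | Possible scores | Unclassified | Eligible at baseline (5 or more) | Unclassified at baseline |
|---|---|---|---|---|
| 1 | 11 | 3 (3/11 = 27.3%) | 6 | 2 (2/6 = 33.3%) |
| 0.5 | 21 | 3 (3/21 = 14.3%) | 11 | 2 (2/11 = 18.2%) |
| 0.1 | 101 | 3 (3/101 = 3.0%) | 51 | 2 (2/51 = 3.9%) |

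At baseline only 7 and 9 count, because a score of 4 fails the entry criterion. The gap at 4 matters mainly after baseline.

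**Step 4: reach.** The descriptive summaries, mixed model and t-test for VAS use the score itself. The improvement tables (14.2.7.2 and 14.2.7.5) are labelled by change in score from baseline, not by change of band. Listing 16.2.6.1 shows each recorded VAS score. Only the shift tables depend on the bands.

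**The case against.** The strongest objection is that the strict signs may not be in the SAP at all. The point rests on one character in three places in machine-read text, and a greater-or-equal sign set as an underlined greater-than sign can lose its underline. The SAP text has other damage: the sentence in section 3.1 giving the mean difference is partly garbled, and bullets come through as assorted symbols. Greater-or-equal signs do survive in section 3.8 (age 30 and over) and in footnote 21 to the schedule of assessments (12 months or more). That argues against a general loss but does not exclude a local one. This part of the objection stands, and it is why the fix begins with the source file.

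A second objection is that the intent is plain: the protocol's bands are complete and the SAP declares no departure from them. That makes the correction easy, but it does not make the printed rule usable. The SAP is the document a programmer follows.

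A third is that little depends on it. VAS is exploratory, the shift-table shell carries no test, and protocol section 15.4.5 already asks for efficacy p-values to be read in an exploratory way. This is right, and it limits the weight of the point.

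A reader might also infer that these scores would be counted as Missing. The documents do not support that. They describe that category as one for missing data and give no rule for a recorded score outside the bands. Missing is one possible result among several.

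**Conclusion.** The point holds as a minor inconsistency. As printed, the SAP's VAS bands leave exactly 4, 7 and 9 without a category, they differ from the protocol without being declared as a change, and the handling of those scores is unspecified. The effect is confined to the descriptive VAS shift tables, 14.2.4.1 to 14.2.4.5.

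The size in affected subjects cannot be worked out from the documents. The figures of 3 of 11 and 2 of 6 hold only for an assumed whole-number scale from 0 to 10; in steps of 0.1 they become 3 of 101 and 2 of 51. It would be wrong to read any of these as the fraction of subjects misclassified, since they count possible values and say nothing about how often each occurs. Nor do the documents support a reading in which the VAS treatment comparisons are at risk, because those use the raw score.

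The conclusion assumes that the source file prints the strict signs. If it prints greater-or-equal signs, the inconsistency disappears.

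**What to change.** 1. Open the SAP source file and look at the three lower bounds in the VAS list in section 4.3.1. If they are greater-or-equal signs, the bands need no change.
2. If they are strict, set the bands to the protocol's: 0; above 0 and below 4; at least 4 and below 7; at least 7 and below 9; at least 9.
3. Add a sentence, or a footnote to the shift-table shell, reserving Missing for scores that were not recorded.

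The cost is three characters and one sentence. No new data are needed, no score other than 4, 7 and 9 changes category, and no analysis outside the VAS shift tables is touched.

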#### IGA score:

0 = Clear

1 = Almost Clear

2 = Mild Disease

3 = Moderate Disease

4 = Severe Disease

A shift table for baseline to each post baseline visit by treatment group will also be created for EASI, VAS, and IGA scores. Shift tables will also be presented by subgroups.

The proportion of subjects with improvement in EASI. IGA and VAS from Baseline to Day 14, Day 28 and Day 42 in the B244 and Vehicle groups will be tabulated. The proportions will be compared using Pearson's Chi-square test of independence. The p-value should be evaluated at

25

a significance level of 0.05. The proportion of subjects with no improvement and the proportion of subjects whose score worsened will also be tabulated for each visit and for each score.

#### 4.3.2. Skindex 16 score:

The Skindex 16 score – average of all 16 items in the scale will be summarized using descriptive statistics at Baseline, Day 14, Day 28, and Day 42 for actual values and change-from-baseline values for both ITT and PP populations.

The three subscores – Symptom subscale (average of items 1-4), Emotional subscale (average of items 5 -11), Functional subscale (average of items 12 -16) will also be summarized similarly.

The difference in treatment groups in change-from-baseline values at post-baseline visits will be analyzed using a mixed model Analysis of Variance similar to as described for the EASI score. The above analysis will also be performed by subgroups - age, race, and gender for the ITT population.

### 4.3.3. Actigraphy Watch

The actigraphy data will be used to determine the estimates of actigraphy movement count per hour, total sleep time (TST), total wake time (TWT), total number of scratching events, scratching events per hour and sleep efficiency(%) each night for only 'Major Rest' periods. 'Rest' periods will not be analayzed as they may or may not indicate the sleep time of the subject. Night averages will be calculated for each parameter from hourly readings. Weekly averages for each parameter will be calculated from the nightly averages. Change in all the three parameters – weekly averages from baseline to week 1, 2, 3 and 4 will be summarized by treatment group and visit. One-sided two-sample equal-variance t-test will be performed to analyze the differences in treatment group means in change from baseline at each post baseline week for each parameter. Non parametric Mann-Whitney U test will also be performed to account for any concerns about the normality of the data.

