9 ACTIGRAPHY WATCH

At Baseline visit, subjects will be provided two actigraphy watches in order to accurately monitor subject's sleep, activity and itching patterns. Subjects will be asked to wear one watch on each wrist 24 hours a day starting with the Baseline visit through Week 4 visit. Actigraphy watches are water resistant and may be left on when bathing/showering/swimming. However, for convenience, subjects may remove watches during the above mentioned procedures but will be asked to put watches back on once these procedures have been completed.

Any deviations will be recorded in the CRF.

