11.6.3 Study Day 1-Baseline visit (-1 to 0)

- inclusion and exclusion criteria
- perform Hanifin and Rajka criteria assessment
- current medications
- obtain in clinic BP and HR
- EASI assessmentVAS assessment
- Skindex 16 questionnaire
- IGA scoring assessment
- dispense actigraphy watches and educate subjects on its use
- allocation of a randomized treatment kit number via IWRS
- delivery of the corresponding pack of Investigational Product
- obtain study medication weight for Investigational Product compliance
- first application of Investigational Product (under medical supervision)
- Microbial content
- study counseling
- study diary counseling
- replenish cleanser and moisturizer when needed
- obtain skin swabs
- blood for biomarkers
- AE monitoring

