12.11 Actigraphy Watch

Subjects will be asked to wear two Actiwatch Spectrum watches on each wrist for the duration of the study, starting with the Baseline visit. The device is the size of a wrist watch, is water resistant, and has a plastic wrist band that is hypoallergenic so it is not likely to cause any skin problems. The device has been used by thousands of research subjects in hundreds of clinical trial with no significant problems for the subjects. Two watches will be given to subjects at Baseline visit. Subjects will be asked to put both watches on their wrists during the visit and wear both watches at all times until Day 28 visit. Subjects will be allowed to take watches off for bathing, swimming and/or work or other activities prohibiting wear of such equipment. Study site personnel will go over the procedures with each patient making sure patient understand the procedures. The actigraphy data will be used to determine the estimates of total sleep time (TST) and total wake time (TWT) each night.

Upon the start of the study, Philips will provide each site with training and provide each site with the number of devices it needs, monitor the battery status of each device and replace as needed, and provide a 24/7 help desk.

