- 6. Weight of an IP kit will be obtained at the at the Baseline visit. Study staff will be asked to weigh 2 bottles without the carton box PRE FIRST DOSE. Weight will be recorded in grams. Subjects will be asked to bring both bottles back for the Week 2 and Week 4 visit. Upon return for the study visit, 2 bottles will be weighted again.
- 7. Subjects will be asked to apply the IP twice daily. First IP application will happen in the office under medical supervision.
- 8. AEs will be monitored throughout the trial, starting with the time ICF has been signed.
- 9. Cleanser and moisturizer should be returned to the study coordinator. Subjects will be asked to go back to their regular routine.
- 10. Actigraphy watch is dispensed at the Baseline visit. Subjects will be asked to wear one watch on each wrist starting at Baseline and through Day 28 visit. Subjects are allowed to take watches off during bathing/swimming/showering but will be asked to put watches back once these procedures are completed.
- 11. Patients should fast for at least 8 hours before the test. Blood for clinical chemistry will be shipped to the central lab for processing. Chemistry, Hematology, HbA1C, Lipid Panel and Angiotensin converting enzyme tests will be done at Screening, Week 2, Week 4 and Week 6. Serology will only be done at Screening. Kits and lab manuals will be provided by the Cenetron Labs.
- 12. Blood samples for biomarkers will be collected and processed on site within 5 minutes of collection. Patients should fast for at least 8 hours before the test. Samples will then be frozen onsite and shipped on monthly bases to the Central lab for storage.
- 13. Blood pressure readings will be obtained at every visit. Subject should be allowed to rest for > 5 minutes sitting, then serial clinic BP measurements and heart (x3) rate will be performed, using the non-dominant arm with a calibrated electronic sphygmomanometer. The average of the second and third readings will be documented.
- 14. Moisturizer to be used for the duration of the trial will be provided to all subjects starting with the Washout period. Subjects will be asked to refrain, if possible, from using any other moisturizer and apply the provided product while they are participating in the trial. Any left over moisturizer will be collected at Week 4 visit.

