#### 3.4. Baseline Definitions

For all analyses, baseline will be defined as the most recent measurement prior to the first administration of study drug. The day of first dose of study medication is Day 0 in the Schedule of Assessments (SOA) and will be considered Relative Study Day 1.

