### 3.10. Missing, Unused, and Spurious Data

In general, there will be no substitutions made to accommodate missing data points. All data recorded on the case report form will be included in data listings that will accompany the clinical study report.

When tabulating adverse event data, partial dates will be handled as follows. If the day of the month is missing, the onset day will be set to the first day of the month unless it is the same month and year as study treatment. In this case, in order to conservatively report the event as treatment-emergent, the onset date will be assumed to be the date of treatment. If the onset day and month are both missing, the day and month will be assumed to be January 1, unless the event occurred in the same year as the study treatment. In this case, the event onset will be coded to the day of treatment in order to conservatively report the event as treatment-emergent. A missing onset date will be coded as the day of treatment.

In all cases, the resulting date will be compared to the AE end date, if present. If the imputed start date is later than the AE end date, then the start date will be set equal to the end date. The imputed start date is used only for determining treatment emergence; data listings will present the partial date as recorded on the CRF.

Missing AE severities will not be imputed and will be considered missing in any tabulations of AE severity. When relation of AEs to the study drug is missing, the AE will be considered "related" to study drug.

22

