# Repeat Table 14.2.8.1 for the following tables:

Table 14.2.8.2 Summary of Values and Change from Baseline for Skindex 16 Score (PP Population)

Table 14.2.8.3 Summary of Values and Change from Baseline for Skindex 16 Score by Gender (ITT Population)

Table 14.2.8.4 Summary of Values and Change from Baseline for Skindex 16 Score by Age Category(ITT Population)

Table 14.2.8.5 Summary of Values and Change from Baseline for Skindex 16 Score by Race (ITT Population)

Table 14.2.8.6 Summary of Values and Change from Baseline for Skindex 16 Score by Number of Atopic Dermatitis Sites (ITT Population)

 p-value is from t-test.

Confidential

Page 1 of x

Table 14.2.9.1

Summary of Values and Change from Baseline for Actigraphy Movement (ITT Population)

Parameter: Total Sleep Time

Visit	Actual/ Change	Statistic	B244 (N=xx)	Placebo (N=xx)	Overall (N=xx)
Baseline	Actual	n	XX	XX	xx
		Mean (SD)	xx.x (xx.xx)	xx.x (xx.xx)	xx.x (xx.xx)
		Median	xx.x	XX.X	XX.X
		Min, Max	xx, xx	XX, XX	xx, xx
Week 1	Actual	n	XX	XX	xx
		Mean (SD)	xx.x (xx.xx)	xx.x (xx.xx)	xx.x (xx.xx)
		Median	XX.X	XX.X	XX.X
		Min, Max	XX, XX	XX, XX	xx, xx
	Change	n	XX	xx	XX
		Mean (SD)	xx.x (xx.xx)	xx.x (xx.xx)	xx.x (xx.xx)
		Median	XX.X	xx.x	xx.x
		Min, Max	XX, XX	XX, XX	xx, xx
		p-value [1]	X.XXXXX		
		p-value [2]	X.XXXX		

 p-value is from t-test.

Source: DIMMINIT

Programming Note: Repeat for parameters: Total Wake time, Average movement count, Total Number of scratching events, Scratching events per hour, sleep efficiency (%) and for all weeks (week 1, 2,3 and 4).

DATE: HH:MM/DDMMMYYYY

Repeat Table 14.2.9.1 for the following tables:

Table 14.2.9.2 Summary of Values and Change from Baseline for Actigraphy Movement (PP Population)

 p-value is from Mann-Whitney U test.

AOBiome Therapeutics Confidential Protocol ADB244-001

Page 1 of x

DATE: HH:MM/DDMMMYYYY

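### The SAP tests night-time actigraphy as change from a pre-dose baseline, but the watches are first worn from the visit at which the first dose is given, so there is no pre-dose night (at most one)

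*SAP*

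**What the plan says.** **The analysis.** SAP 4.3.3 uses only the main night-time rest periods. It averages hourly readings to nights and nights to weeks. Of the change in these parameters it says that "weekly averages from baseline to week 1, 2, 3 and 4 will be summarized by treatment group and visit". The arms are then compared on change from baseline at each week, by a one-sided equal-variance t-test and a Mann-Whitney U test. The shell for Table 14.2.9.1 has a Baseline row, then Actual and Change rows from Week 1, with both p-values under Change. Its repeat note asks for the same table in the PP population (Table 14.2.9.2).

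**The baseline.** SAP 3.4 states that for all analyses "baseline will be defined as the most recent measurement prior to the first administration of study drug". SAP 4.3.3 makes no exception for actigraphy.

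**The watches.** Protocol section 9: "Subjects will be asked to wear one watch on each wrist 24 hours a day starting with the Baseline visit through Week 4 visit". Protocol 12.11 asks subjects to "put both watches on their wrists during the visit and wear both watches at all times until Day 28 visit".

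**The first dose.** Protocol 11.6.3 lists the first application among the Baseline visit procedures, and note 7 of Appendix A says: "First IP application will happen in the office under medical supervision".

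**Missing data and changes.** SAP 3.10: "In general, there will be no substitutions made to accommodate missing data points". SAP section 5 defers the biomarker and microbial data and does not mention actigraphy.

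**The concern.** A change from baseline needs a value recorded before treatment, on the same footing as the later values. Here the later values are averages of night-time recordings, and recording begins at the visit where treatment begins. A short spell of daytime wear in the clinic before dosing does not help, because such data are outside the analysis.

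If the SAP is followed literally, the between-arm tests for the sleep and scratching objective have nothing to work on; only untested weekly values by arm remain. If instead a post-dose night is taken as baseline during programming, SAP 3.4 is contradicted and part of any early treatment effect may be subtracted from the comparison. The plan authorises no such choice, so it would be made outside the plan.

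**Working it through.** The documents give no sample size, SD or expected effect for actigraphy, so there is no planned figure to reproduce. The power statement concerns EASI and does not bear on this point. The check is one of timing, followed by a count of the affected output.

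**1. When recording starts.** In the Appendix A schedule the watch row is marked at Baseline (dispensed), Day 28 (returned) and Early Termination (returned). Screening and Washout carry no mark. Protocol 9, 11.6.3 and 12.11 and note 10 of both schedules agree with this.

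**2. When dosing starts.** At the Baseline visit, in the clinic (Protocol 11.6.3; Appendix A note 7). The visit window is Day -1 to Day 0. SAP 3.4 places the first dose at Day 0 of the schedule.

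**3. Pre-dose nights.** Nights = day of first dose − day the watches go on, with both days inside the visit window:

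| Watches on | First dose | Pre-dose nights |
|---|---|---|
| Day -1 | Day -1 | 0 |
| Day 0 | Day 0 | 0 |
| Day -1 | Day 0 | 1 |

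The third row requires the visit to be split over two days, which neither document describes.

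**4. Could a post-dose night stand in?** From a Day 0 visit to Day 28 there are 28 nights, or 27 to 29 with the ±1 day window, and all follow the first dose. If a week is seven nights (an assumption, since the SAP does not define the actigraphy week), weeks 1 to 4 take 4 × 7 = 28 nights. A first night used as baseline would therefore normally also sit inside the week 1 average that it is subtracted from.

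**5. Affected output.** SAP 4.3.3 and the programming note to Table 14.2.9.1 cover six parameters: movement count, total sleep time, total wake time, number of scratching events, scratching events per hour and sleep efficiency. With two populations:

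- Baseline rows: 6 × 2 = 12
- Change rows: 6 × 4 weeks × 2 = 48
- p-values: 48 × 2 tests = 96

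SAP 4.3.3 also refers to three parameters when it describes the change analysis. On that reading the counts are 3 × 2 = 6, 3 × 4 × 2 = 24 and 24 × 2 = 48.

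**The case against.** The best counter-argument is that the analysis is not strictly impossible. SAP 3.4 asks only for the most recent pre-dose measurement, not for a week of them. A visit begun on Day -1 with dosing on Day 0 fits the window and would yield one night, from which a change could be computed. That much stands, and it is why the range is 0 to 1 rather than 0. It does not rescue the plan. Watch fitting and first application are listed under a single visit, no text provides for splitting it, and a one-night baseline set against weekly averages would exist only for the subjects whose visit happened to be split.

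Three smaller points are fair:

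- SAP 3.10 is a general rule about missing values. That it leads to empty cells when a baseline was never scheduled is an inference, though nothing in the SAP points elsewhere.
- The row and p-value counts measure output, not an effect on any conclusion. They also include the PP table, which appears in the repeat note but not in the SAP's table list, and which SAP 4.3 would drop if the PP and ITT populations coincided.
- The endpoint is exploratory, and Protocol 15.4.5 already asks for p-values to be read that way.

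These points limit how much the defect matters; they do not remove it.

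**Conclusion.** The concern holds. Read together, SAP 3.4, SAP 4.3.3 and the protocol's visit procedures leave no pre-dose night for a subject seen on one day, and at most one if the visit is split. The planned change-from-baseline tests for actigraphy therefore cannot be run as defined. The consequence is confined to an exploratory objective, for which all the planned between-arm tests are affected. The safety and EASI analyses do not depend on it. The bias from substituting a post-dose baseline cannot be sized, because no actigraphy SD or effect is given.

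The conclusion rests on the Baseline visit being held as the protocol lists it. The remark about overlap with week 1 also assumes seven-night weeks. The change should be made, but it is not critical to the trial.

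**What to change.** Before unblinding, in SAP 4.3.3 and Tables 14.2.9.1 and 14.2.9.2:

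1. Remove the Baseline and Change rows.
2. Compare the weekly averages for weeks 1 to 4 directly between the randomised arms, with the t-test and Mann-Whitney test already planned. Randomisation makes this comparison valid without a baseline.
3. Report the difference in means with its confidence interval, which the present shell lacks.
4. Record in SAP section 5 that this departs from the Baseline to Day 28 actigraphy endpoint in Protocol 4.3 because no pre-dose recording period exists. The entry should also name the matching wording in Protocol 3.3 and SAP 1.1.2.3 and 1.2.4.1.

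Defining a special actigraphy baseline instead is less attractive: for a one-day visit it could only be a post-dose value.

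The cost is SAP text, two table shells and one entry in section 5, with no new data. The price is that there is no individual baseline to adjust for, so precision may be somewhat lower than with a true pre-dose baseline.
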